2.9 Sample size justification

We hypothesize that TPT prescribing will be 65% in routine TUTT implementation and 80% in TUTT-PT implementation. Thus, we will enrol 200 PLHIV in TUTT clinics and 200 PLHIV in clinics where they will receive TUTT-PT (450 total) in order to detect this difference with 80% power at a 5% level of significance while accounting for clustering by clinic (a design effect of approximately 1.3). A sample size of 450 will also enable us to identify an estimated 20 new ART clients diagnosed with TB (assuming prevalence of 5%) in order to evaluate time to TB treatment initiation. In addition, throughout study implementation, we will conduct ongoing monitoring of intervention safety, defined as the number of participants diagnosed with TB who remain on TPT after diagnosis by study arm.

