2.4 Clinic selection

Among the 18 public sector health facilities that participated in Fedisa in the [name] district, 5 will be selected to participate in the study from the list of clinics below. Clinics were chosen based on the average number of PLHIV who initiated or re-initiated ART on a monthly basis in 2021 and 2022. In order to ensure we can achieve the required sample size; we will select the larger clinics (on the basis of ART (re-)initiations) for study participation. Among the five selected clinics, two clinics will be assigned to standard TUTT implementation, and three clinics will be assigned to TUTT-PT implementation.

District	Clinic	ART initiations 2021	Mean monthly initiations 2021	ART initiations 2022	Mean monthly initiations 2022
Matlosana	Majara Sephapho	230	19.2	133	14.8
Matlosana	Orkney	207	17.25	130	14.4
Matlosana	Gateway NM Pretorius PHC	201	16.8	104	11.6
Matlosana	Kanana	194	16.2	114	10.4
Matlosana	Alabama	159	13.25	162	13.5
Matlosana	Tsholofelo	146	12.2	118	9.8
Matlosana	Empilisweni	144	12	102	11.2
Matlosana	Khuma	120	10	109	9.1

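### Section 2.9 gives arm sizes that sum to 400 but a total of 450, so the enrolment target is ambiguous and 50 participants have no arm

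*Combined protocol and SAP*

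**What the plan says.** All of the enrolment figures are in section 2.9 (Sample size justification).

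- **Effect assumed:** "TPT prescribing will be 65% in routine TUTT implementation and 80% in TUTT-PT implementation".
- **Enrolment:** "we will enrol 200 PLHIV in TUTT clinics and 200 PLHIV in clinics where they will receive TUTT-PT (450 total").
- **Error rates:** the aim is to "detect this difference with 80% power at a 5% level of significance". The text does not say whether the test is one- or two-sided, or whether a continuity correction was used.
- **Clustering:** the calculation is described as "accounting for clustering by clinic (a design effect of approximately 1.3").
- **TB yield:** "A sample size of 450 will also enable us to identify an estimated 20 new ART clients diagnosed with TB", at an assumed prevalence of 5%. This count is the stated basis for evaluating time to TB treatment initiation, which section 2.8 lists as a primary outcome.

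Section 2.4 (Clinic selection) adds that "two clinics will be assigned to standard TUTT implementation, and three clinics will be assigned to TUTT-PT implementation". It gives no number of participants per arm.

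**The concern.** The paragraph that sets the size of the study carries two totals. The arm figures imply 400. The total is given as 450, and because it is repeated in the next sentence it cannot simply be dismissed as a single typing slip. The TB count sits in the sentence that cites 450 but equals 5% of 400.

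As written, recruitment could end at 400 or at 450 and either could be called the planned number. If it runs to 450, the text does not say which arm takes the additional 50. The TB yield supporting a primary outcome is also tied to a total it does not match.

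**Working it through.** **Inputs, all from section 2.9:** control proportion p1 = 0.65; intervention proportion p2 = 0.80; difference d = 0.15; power 80%; significance level 5%; design effect 1.3; arms 200 and 200; total 450; TB prevalence 5%; 20 TB cases. A two-sided test is my assumption (z = 1.960 for the level, 0.842 for power).

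**1. Total.** 200 + 200 = 400. The gap is 450 − 400 = 50, and 50/400 = 12.5%.

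**2. TB cases.** 0.05 × 400 = 20.0, as stated. 0.05 × 450 = 22.5. Twenty cases in 450 would be a prevalence of 20/450 = 4.4%.

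**3. Can 200 per arm be reproduced?** With pooled variance under the null and p̄ = (0.65 + 0.80)/2 = 0.725:

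n = [1.960·√(2·0.725·0.275) + 0.842·√(0.65·0.35 + 0.80·0.20)]² / 0.15²

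= (1.2377 + 0.5239)² / 0.0225 = 137.9, so 138 per arm.

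With continuity correction:

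n' = (n/4)·[1 + √(1 + 4/(n·d))]² = 150.95, so 151 per arm.

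Multiplying by the design effect:

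| Version | Per arm | × 1.3 | Rounded up | Total |
|---|---|---|---|---|
| Uncorrected | 138 | 179.4 | 180 | 360 |
| Continuity-corrected | 151 | 196.3 | 197 | 394 |

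The corrected version reproduces 200 per arm to within 3 participants.

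**4. Can 450 be reproduced?** I varied the TUTT-PT to standard ratio over 1, 1.25, 0.8 and 1.5; the last of these is the 3:2 ratio of clinics.

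| Test | Totals, uncorrected | Totals, continuity-corrected |
|---|---|---|
| Two-sided | 360 to 372 | 394 to 407 |
| One-sided | 284 to 293 | 318 to 329 |

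None reaches 450. Inflating 400 for attrition would need a loss of 1 − 400/450 = 11.1%, and section 2.9 states no attrition allowance.

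**5. Power at each total**, with arm sizes divided by 1.3 and the same pooled-null formula:

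| Standard + TUTT-PT | Total | Uncorrected | Continuity-corrected |
|---|---|---|---|
| 200 + 200 | 400 | 84.1% | 80.8% |
| 225 + 225 | 450 | 88.1% | 85.5% |
| 200 + 250 | 450 | 87.9% | 85.3% |
| 250 + 200 | 450 | 87.6% | 84.9% |
| 180 + 270 | 450 | 87.1% | 84.4% |

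For 200 + 200, the null standard error is 0.0509, the alternative standard error is 0.0502 and the correction term is 0.0065. Uncorrected: (0.15 − 1.960·0.0509)/0.0502 = 1.00, giving 84.1%. Corrected: (0.15 − 0.0065 − 1.960·0.0509)/0.0502 = 0.87, giving 80.8%.

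**The case against.** The strongest reply is that this is a small slip in a study that calls itself a non-randomised pilot and says its inferences will be limited. Each arm has an explicit target of 200. The arm figures, the TB count and the stated power all agree with 400, and only the total is out of line. The TB yield is labelled an estimate and differs by 2.5 cases, whereas the 5–8% positivity range in the background summary moves the yield at 400 from 20 to 0.08 × 400 = 32. No precision target rests on 20 rather than 22 or 23, and no planned analysis changes between 400 and 450.

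Most of this stands, and it limits the point to an ambiguous target. It does not remove the contradiction: the figure labelled as the total is the one without support, and it is stated twice. The 20 cases alone would be weak evidence for 400, since 22.5 might have been loosely rounded, but together with the arm sizes and the sample-size calculation they point the same way.

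Three stronger readings are tempting, and the documents do not support them:

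- **That the stated 80% power fits neither total.** At 200 + 200 with continuity correction the power is 80.8%, which matches. Section 2.9 does not rule that version out.
- **That there is no recruitment target at all.** The arm targets are explicit. The ambiguity is between two totals.
- **That the 2:3 clinic split means 200 + 250 was intended.** Section 2.4 allocates clinics, not participants, and section 2.9 says 200 for both arms.

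**Conclusion.** The inconsistency is real and needs correcting. Section 2.9 supports 400 through its arm sizes, its TB count and its power calculation, but states 450 as the total. The size of the discrepancy is 50 participants and 2.5 expected TB cases.

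A reader might infer that the study is underpowered at the lower figure. It is not on the plan's own assumptions: every split in the table exceeds 80%, with or without continuity correction. The harm is a misstated sample size and TB yield.

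The conclusion assumes a two-sided 5% test and takes the design effect of 1.3 as given; whether 1.3 suits five clinics is a separate question, not tested here. The sum of the arms and the TB count depend on neither assumption. I did not have all of the front matter, so I cannot exclude a further sample-size statement there, but it would not remove the contradiction within section 2.9.

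**What to change.** State one total that equals the sum of the arm targets, in one of two ways:

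- **If 400 is intended:** write 200 + 200 = 400 and replace 450 in both places. The 20 expected TB cases then stand. Power is about 84% uncorrected or 81% with continuity correction.
- **If 450 is intended:** give arm sizes that sum to 450 and the reason for the extra 50 (such as attrition or unequal arms). Change the expected TB cases to about 22–23, and restate power for that split (about 87–88% uncorrected).

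Either way, say whether the test is two-sided and whether a continuity correction was used, so that the figure can be reproduced.

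The edit is one or two sentences, but not free of process: section 7.1 requires agreement from co-investigators at both sites, and the consent text following section 7.4 requires Ethics Committee/IRB approval for changes in the research. Choosing 400 adds no participants. Choosing 450 means 50 more than the current arm targets provide.

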Background: The overarching goal of this proposal is to contribute to safely increasing TB preventive therapy (TPT) uptake in the context of a new South African policy of universal TB testing at ART initiation. TB is the leading infectious cause of death globally; South Africa has one of the highest incidences of TB worldwide (513 cases/100,000 individuals in 2021).¹ TPT forms a cornerstone of World Health Organization (WHO) and South African TB control guidelines. The Fedisa PreventTB study (R01AI150432) is testing a behavioural economics approach to increase TPT prescribing to people living with HIV (PLHIV) in a cluster-randomized trial in 36 public-sector health facilities in South Africa. In preliminary analyses, we have observed overall TPT delivery reaching 51% of PLHIV (among 52,000 patients assessed). While the study is ongoing, the combined data show a marked year to year increase in TPT prescribing at ART initiation from approximately 23% in 2017 to 69% in 2022. Although receipt of TPT has increased, barriers remain.

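### Equal arm targets from two standard and three TUTT-PT clinics, with no accrual rule, leave either enrolment period or capture fraction unbalanced; the likely calendar bias is small and cheap to prevent

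*Combined protocol and SAP*

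**What the plan says.** - **Targets (2.9 Sample size justification).** "we will enrol 200 PLHIV in TUTT clinics and 200 PLHIV in clinics where they will receive TUTT-PT". The same sentence puts the total at 450, which is not 200 + 200. The planning assumption is that "TPT prescribing will be 65% in routine TUTT implementation and 80% in TUTT-PT implementation", "with 80% power at a 5% level of significance while accounting for clustering by clinic (a design effect of approximately 1.3").
- **Clinics (2.4 Clinic selection).** "Among the five selected clinics, two clinics will be assigned to standard TUTT implementation, and three clinics will be assigned to TUTT-PT implementation". Eight candidates are tabulated and "we will select the larger clinics (on the basis of ART (re-)initiations) for study participation". The section does not say which clinics go to which arm.
- **Timing (section 3, timeline).** There is one recruitment row, 2024 Q1 to Q4, not divided by arm. No section gives per-clinic targets, pacing, consecutive enrolment, a common closing date, or a rule on whether an arm stops when it reaches its target.
- **Analysis (2.8, Table 1).** The TPT-within-7-days outcome is compared by chi-square. No calendar term is listed.
- **Background.** The opening summary reports a "marked year to year increase in TPT prescribing at ART initiation from approximately 23% in 2017 to 69% in 2022". It also says that universal TB testing was introduced in 2023 with conflicting guidance on when to start TPT.
- **Limitations (section 5).** Non-randomisation and consent-related selection are named. Calendar time and differential accrual are not.

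**The concern.** Two clinics have to supply as many participants as three. Unless the two are much busier, they either take longer or must enrol a larger share of their clients.

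If they take longer, the last part of the standard arm has no concurrent TUTT-PT enrolment. Part of the measured difference is then calendar time, in a setting where TPT practice has been moving.

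If they enrol a larger share, the arms may contain differently selected clients. Selection matters here because the arms enrol at different points. Under 2.6, standard-arm clients reach the study nurse after the clinic's prescribing decision. Under 2.5, TUTT-PT clients are enrolled before the referral for TPT. Selective capture in the standard arm could therefore follow the primary outcome itself.

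An unadjusted chi-square removes neither effect.

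**Working it through.** **1. The plan's own figure.** For 65% versus 80%, two-sided 5% (sidedness assumed) and 80% power, n per arm is 138 uncorrected or 151 with continuity correction. Multiplying by 1.3 gives 179.4 (180) or 196.3 (197). The second is close to 200, so 200 per arm is reproduced. The total of 450 is not, since 200 + 200 = 400.

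**2. Clinic volumes (2.4 table).** The five largest clinics by 2021 volume, and by both years together, have 2022 monthly means of 14.8, 14.4, 11.6, 10.4 and 13.5, sum 64.7. The extremes of the ten 2/3 splits are:

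| Standard pair | Standard, per month | TUTT-PT, per month |
|---|---|---|
| Smallest | 11.6 + 10.4 = 22.0 | 64.7 − 22.0 = 42.7 |
| Largest | 14.8 + 14.4 = 29.2 | 64.7 − 29.2 = 35.5 |

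TUTT-PT has the larger flow in all ten.

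**3. Shared 12-month window: capture needed = 200 / (12 × monthly volume).**
- Standard: 200/(12 × 29.2) = 57% to 200/(12 × 22.0) = 76%.
- TUTT-PT: 200/(12 × 42.7) = 39% to 200/(12 × 35.5) = 47%.
- At 2021 means the same sum gives 46-57% and 31-36%.

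**4. Equal capture, common start, uniform accrual, standard arm taking 12 months.**
- TUTT-PT fill time = 12 × (standard volume / TUTT-PT volume): 12 × 22.0/42.7 = 6.2 months; 12 × 29.2/35.5 = 9.9 months.
- Difference in mean enrolment date = (12 − fill time)/2: 2.9 and 1.1 months.

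**5. Calendar bias at the documented trend.** (69 − 23)/5 = 9.2 points a year, or 0.77 a month. Then 0.77 × 1.1 = 0.8 and 0.77 × 2.9 = 2.2 points, against the planned 80 − 65 = 15.

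**6. Sensitivity to the unsettled total.**
- At 225 + 225 the ratio of fill times is unchanged.
- At 200 standard + 250 TUTT-PT and full capture, the largest-pair split takes 200/29.2 = 6.8 against 250/35.5 = 7.0 months, so the order reverses. The smallest-pair split takes 200/22.0 = 9.1 against 250/42.7 = 5.9 months, so the gap remains.

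**7. Cost of unequal targets.** Power = Φ{[0.15 − 1.96√(p̄(1 − p̄)(1/a + 1/b))] / √(0.65 × 0.35/a + 0.80 × 0.20/b)}, where a and b are the arm sizes divided by 1.3 and p̄ is the pooled proportion.
- 200:200 gives 84.1%.
- 160:240 (the 2:3 clinic ratio) gives 83.1%.
- Exact proportionality to volume depends on the clinics named. The smallest pair gives 400 × 22.0/64.7 = 136, so 136:264 and 81.0%. The largest pair gives 400 × 29.2/64.7 = 181, so 181:219 and 84.0%.

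**The case against.** **Both imbalances are not inevitable.** A reader might infer that the arms must differ in calendar time and in capture. The arithmetic does not show that: with equal capture the periods differ, and over a shared window the capture differs. The timeline has one recruitment period and never says that an arm closes on reaching its target. Both targets fit that window. This stands; the defect is that the plan leaves the outcome to chance.

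**The modelled fall to 17-31% is not a calendar trend.** A reader might take it as drift and arrive at a bias that rivals the target difference. The opening summary ties that figure to waiting for a sputum result. That is a way of delivering TPT and part of the comparator, not a secular change. Nothing says such a fall would happen within the recruitment year, and 2.9 assumes 65% in standard clinics.

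**The 2022 annual totals do not show that the target is out of reach.** Total divided by monthly mean implies about 9 months for four clinics, 11 for one and 12 for three, so the totals are not on a common basis. Treating them as full-year counts would overstate the capture needed. On the monthly means the worst case is 76%. Putting the table on one basis leaves the five largest clinics by two-year volume unchanged.

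**Capture differences bias the result only if capture is selective.** The documents give no evidence either way, although the different enrolment points in 2.5 and 2.6 make it worth recording.

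**The plan already admits limited inference.** Section 5 does so, and with five non-randomly assigned clinics, clinic-level confounding is the larger threat. That stands. Unlike clinic assignment, though, the accrual problem can be removed without extra participants.

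**Conclusion.** The point holds as a modest, avoidable design weakness. With equal targets, TUTT-PT accrues faster in every split of the five largest clinics. The plan does not determine whether this appears as a calendar gap (1.1-2.9 months in mean enrolment date) or a capture gap (57-76% versus 39-47%), and its primary test addresses neither.

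The calendar effect is about 1-2 points of 15. Its direction is unknown: continued growth in prescribing would raise a later-enrolled standard arm and dilute the difference, while a decline would inflate it.

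These figures assume 200 per arm, 2022 monthly means, uniform accrual from a common start and, for the calendar gap, equal capture with the standard arm taking 12 months. The bias also extends the 2017-2022 trend into 2024, past the 2023 policy change. If 450 means 200 + 250, the imbalance nearly vanishes or reverses for some splits.

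**What to change.** 1. Reconcile 200 + 200 with 450 in 2.9 and state the target for each arm.
2. Open and close enrolment on the same dates in all five clinics, with no arm closing early. This matters more than modelling, because a quarter with participants in only one arm tells the model nothing about the arm difference.
3. Keep the unadjusted chi-square and add an estimate of the primary difference adjusted for calendar quarter.
4. Log and report eligible versus enrolled by clinic and month.
5. Consider arm targets roughly proportional to clinic volume, set once the clinics are assigned. Even monthly pacing towards equal totals would align the dates but build the capture gap in. As an example, 160:240 follows the clinic counts.

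**Cost.** No extra participants. TUTT-PT clinics enrol more slowly than they could. Four quarters add three parameters to a model. At a design effect of 1.3, 160:240 loses about 1 point of power (83.1% versus 84.1%); exact proportionality costs between about 0.1 and 3 points, depending on the clinics assigned.

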2.1 Study design

We are proposing a **non-randomized pilot evaluation** of a universal TPT initiation strategy within the context of TUTT implementation for PLHIV initiating or re-initiating ART. Clinics will be assigned to the novel TUTT-PT arm or standard TUTT implementation arm with the primary analysis focused on the proportion initiated on TPT within 7 days of ART start. This study will also assess the rate of new TB diagnoses, TB treatment initiation for those testing positive for TB, the prevalence of TB drug resistance at the time of TB treatment initiation, time to TPT initiation, and provider experiences with TUTT implementation and TPT provision, among others.

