2.8 Outcomes and analysis

The primary outcomes are the proportion of PLHIV who initiate TPT within 7 days of ART start and the median time to TB treatment initiation for those who test positive for TB. ART initiators include clients who are ART naïve and those re-initiating ART after a lapse in treatment. Secondary outcomes are included in the table below. TB test results and TPT initiation will be ascertained from study source documents and all available data sources in the clinics, including but not limited to paper files, electronic files (Tier.NET and DHIS2), clinic registers, pharmacy records, and lab test results. Analytic approaches are described in the table below.

Table 1. Outcomes & analysis approach

	Outcomes	Data source	Statistical Test
Primary	Proportion of PLHIV who initiate TPT within 7 days of ART (re-)initiation	Paper files, electronic files, clinic registers, pharmacy records, lab test results	Chi-square
Primary	Proportion of PLHIV who initiate TPT and have a subsequent positive TB test result	Paper files, electronic files, clinic registers, pharmacy records, lab test results	Chi-square
Primary	Healthcare provider experiences with universal TB testing and TPT provision	In-depth interviews	N/A
Primary	Median time to TB treatment initiation for those who test positive for TB	Paper files, electronic files, clinic registers, pharmacy records, lab test results	Kaplan-Meier
Secondary	Proportion of PLHIV evaluated for ART (re-)initiation tested for TB within 7 days of ART start, stratified by TB symptom status	Paper files, electronic files, clinic registers, pharmacy records, lab test results	Chi-square
Secondary	Prevalence of active TB disease among PLHIV evaluated for ART (re-)initiation, stratified by symptom status	Paper files, electronic files, clinic registers, pharmacy records, lab test results	Chi-square
Secondary	Median time from ART initiation to TPT initiation	Paper files, electronic files, clinic registers, pharmacy records, lab test results	Kaplan-Meier
Secondary	Proportion of PLHIV diagnosed with TB who remain on TPT for 7 days or longer	Paper files, electronic files, clinic registers, pharmacy records, lab test results	Chi-square
Secondary	Prevalence of TB drug resistance at TB treatment initiation, stratified by TPT use at the time of TB diagnosis	Paper files, electronic files, clinic registers, pharmacy records, lab test results	Descriptive proportions

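### The 80% power statement treats the design effect of 1.3 as known: a clinic-level analysis of five clinics has about 53–57% power, and the chi-square listed in Table 1 does not hold the 5% level

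*Combined protocol and SAP*

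**What the plan says.** The unit of assignment is the clinic, without randomisation (section 2.1): "Clinics will be assigned to the novel TUTT-PT arm or standard TUTT implementation arm". Section 2.4 fixes the number: "two clinics will be assigned to standard TUTT implementation, and three clinics will be assigned to TUTT-PT implementation".

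Section 2.9 gives the effect, "We hypothesize that TPT prescribing will be 65% in routine TUTT implementation and 80% in TUTT-PT implementation", and the size, "we will enrol 200 PLHIV in TUTT clinics and 200 PLHIV in clinics where they will receive TUTT-PT (450 total"). It presents this size as sufficient "in order to detect this difference with 80% power at a 5% level of significance while accounting for clustering by clinic", with "a design effect of approximately 1.3". No ICC, source or number of clinics enters the calculation, and the sidedness of the test is not stated.

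Table 1 in section 2.8 lists a chi-square test for the corresponding primary outcome, "Proportion of PLHIV who initiate TPT within 7 days of ART (re-)initiation". It gives no cluster adjustment or small-sample correction. Section 5 says inference will be limited because the pilot is not randomised. It does not mention the number of clinics.

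**The concern.** Multiplying an individual-level sample size by a design effect and keeping the critical value 1.96 is sound when clinics are many or the between-clinic variance is known. Neither is shown here. If the variance is estimated from 2 + 3 clinics, 5 − 2 = 3 degrees of freedom remain and the two-sided 5% critical value is 3.18.

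The planned test and the sample-size statement also disagree: section 2.9 says clustering is accounted for, while the Table 1 test ignores it. The stake depends on which analysis is run. With a clinic-level test, a real 15-point gain would be missed far more often than the stated 20%. With the chi-square as listed, the main risk is the reverse, a false positive. Either way, section 2.9's pair of 80% power and 5% error is not what the reader gets. Section 1.1.4 says the comparison is meant to inform TPT policy.

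**Working it through.** **Inputs.** p1 = 0.65, p2 = 0.80, design effect (DE) 1.3, 5% level, 80% power (section 2.9); 2 versus 3 clinics (section 2.4); chi-square (Table 1). Section 2.9 gives 200 + 200 but a total of 450, so both 200 and 225 per arm are shown. Two-sided testing is assumed. No dropout is stated and none is applied.

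**1. The plan's own figure.** The two-proportion formula gives 138 per arm, or 151 with continuity correction. Times 1.3:
- 138 × 1.3 = 179.4
- 151 × 1.3 = 196.3, so 197 per arm, against 200 stated

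Run the other way, without continuity correction, power is 84% at 200 per arm and 88% at 225. The stated size reproduces.

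**2. The same design with 3 df.** Let SE = √[DE × (p1(1 − p1) + p2(1 − p2))/n], with 0.65 × 0.35 = 0.2275 and 0.80 × 0.20 = 0.16.
- 200 per arm: SE = √(1.3 × 0.3875/200) = 0.0502; noncentrality 0.15/0.0502 = 2.99; noncentral-t power 53.0%.
- 225 per arm: SE = √(1.3 × 0.3875/225) = 0.0473; noncentrality 3.17; power 57.5%.
- One-sided 5%: 73% and 77%.
- A total of 450 split 200/250 or 180/270: 55–57%.

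A beta-binomial simulation of an unweighted clinic-level t-test (200,000 runs per setting) gives 53–58% across these allocations.

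**3. The listed chi-square.** In the same simulation, at the ICC that matches DE 1.3 with 80 per clinic (0.3/79 = 0.0038), power at 200 per arm is 89% and the null rejection rate 8.7%. At 225 per arm they are 92% and 9.2%.

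The null rate can be checked by hand. With 100 and 66.7 per clinic, the arm design effects are 1 + 99 × ICC and 1 + 65.7 × ICC. With equal proportions the variance is inflated by their mean, and the rejection rate is 2[1 − Φ(1.96/√mean DE)].

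| ICC | Arm DEs | Mean DE | Null rejection |
|---|---|---|---|
| 0.0038 | 1.376, 1.249 | 1.31 | about 9% |
| 0.01 (assumed) | 1.99, 1.66 | 1.82 | about 15% |
| 0.02 (assumed) | 2.98, 2.31 | 2.65 | about 23% |

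**4. Chi-square divided by 1.3.** Simulated power is about 84% at 200 per arm and 88% at 225, with null rejection of about 5%. This recovers the plan's figures, but only if 1.3 is right.

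**5. What 1.3 implies.** ICC = 0.3/(m − 1) is 0.0030 at 100 per clinic and 0.0046 at 66.7. True clinic rates would then have an SD of √(ICC × 0.2275), about 2.6 to 3.2 percentage points. The documents neither support nor contradict this.

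**6. Expected 95% interval half-width, 3.182 × SE.**
- DE 1.3: 3.182 × 0.0502 = 16.0 points (200 per arm); 3.182 × 0.0473 = 15.1 points (225 per arm).
- ICC 0.01 (assumed), 200 per arm: SE = √(1.99 × 0.2275/200 + 1.66 × 0.16/200) = 0.0599; 19.1 points.
- ICC 0.02 (assumed), 200 per arm: SE = √(2.98 × 0.2275/200 + 2.31 × 0.16/200) = 0.0724; 23.0 points.

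**The case against.** The strongest reply is that section 2.9 contains no arithmetic error and that the 53–57% belongs to a test the plan does not name. Both parts are true. The sum reproduces, and under the listed chi-square power is about 90%. But that power comes with about 9% false positives at the plan's own design effect, so the chi-square does not deliver the stated 5% level. Dividing it by 1.3 would restore both figures, but the plan does not specify this, and it would rest wholly on an unsourced value.

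A second reply is that this is a pilot whose limited inference is admitted. That lessens the consequence. It does not make an explicit power statement for a primary outcome correct, and section 5 bases the limit on non-randomisation alone.

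A reader might go further in three ways that the documents do not support:
- **That the study as planned will miss a real effect about half the time.** That applies to a 3-df analysis. Under the test as listed, the larger risk is a false positive.
- **That more patients in the same five clinics would help little.** Holding the ICC at 0.0038 and letting the design effect grow with clinic size, 3-df power rises from 53% at 200 per arm to about 72% at 400. The statement is roughly true only at an ICC of 0.02 or above (31% to 36% on doubling), and the documents give no such ICC.
- **That significance is impossible because a permutation test over the 10 possible 2-versus-3 allocations cannot give p below 0.10.** The plan proposes no such test, and the clinics are not randomised.

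**Conclusion.** The concern holds in this form: section 2.9's 80% power at a 5% level, with clustering accounted for, is right only if the design effect is known to be 1.3. A two-sided analysis that estimates clinic variance from the five clinics has about 53% power (200 per arm) to 57% (225 per arm). One-sided testing does not rescue the claim. The Table 1 chi-square keeps high power only by letting the error rate rise to about 9%, or to about 15% and 23% at ICCs of 0.01 and 0.02. Those two ICCs are assumptions, shown for range. The results at design effect 1.3 use the plan's own inputs, with two-sidedness assumed where stated.

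The defect is an omitted degrees-of-freedom penalty plus a mismatch between sections 2.8 and 2.9. It is not a wrong sum, and it does not show that the study cannot yield a useful estimate.

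**What to change.** 1. In section 2.9, replace the 80% power statement with one of two figures. The first is the power of a clinic-level analysis with 3 df: about 53–57% at design effect 1.3, depending on whether 400 or 450 is the intended total. The second is the expected 95% interval half-width: about 15–16 points at design effect 1.3, and about 19 and 23 points at assumed ICCs of 0.01 and 0.02. State whether the test is one- or two-sided.
2. In Table 1, change the test for TPT initiation within 7 days to a clinic-level analysis with 3 df, so that sections 2.8 and 2.9 describe the same analysis.
3. Support the design effect with an ICC from existing Fedisa clinic data. Estimate it within trial arm and for a recent period, because the background reports prescribing rising from about 23% in 2017 to 69% in 2022. A pooled estimate could mix arm and calendar-time differences with clinic variation. Much of that period also precedes the 2023 testing policy, which should be noted.
4. In section 5, name the small number of clinics as a limit on power and precision, separate from non-randomisation.

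The cost is a reworded paragraph, one table entry, one limitation and one ICC estimate. The stated figure becomes less favourable and the intervals wider. No extra patients or clinics are needed. Whether to renounce significance-based conclusions altogether is a matter of preference and is not needed to correct the statement.
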